## 1.2 Rationale for Vesigenurtacel-L Development

The hypotheses behind the development of vesigenurtacel-L (HS-410), a therapeutic vaccine, to treat urothelial cancer of the bladder are as follows:

(1) A range of tumor-associated antigens (survivin, LAGE-1, MAGE-A3, MAGE-A11, and PRAME) have been identified in bladder cancer, and it is postulated that treatment with BCG therapy provides the innate immune system with a warning signal to induce and direct an acquired immune response against such antigens. However, BCG therapy is accompanied by a high failure rate and significant side effects, which limit its clinical application. The clinical response to BCG might be improved through concurrent enhancement of tumor immunogenicity by concomitant administration of a vaccine, such as vesigenurtacel-L, during standard BCG therapy.

(2) Secreted gp96-Ig from vesigenurtacel-L combines adjuvant activity with polyvalent peptide specificity. Vesigenurtacel-L activates dendritic cells (DC), natural killer (NK) cells, and cytotoxic T lymphocytes (CTL). Tumor cells can be killed by NK cell-specific mechanisms, by promiscuous killing by CD8+ CTL through NKG2D, and by major histocompatibility complex (MHC)-restricted CD8+ CTL activity. The activation of DC and NK cells by vesigenurtacel-L may also counteract the generation of immunosuppressive CD4+ regulatory cells.

(3) Vesigenurtacel-L also stimulates antigen cross presentation via the CD91 receptor, Toll-like receptor (TLR) 2 and TLR4 on DC and macrophages. Allogeneic tumor cells are likely to share public tumor antigens in analogy to melanoma. Therefore, allogeneic, gp96-secreting tumor cells used as a vaccine (such as vesigenurtacel-L) are expected to generate NK cell and CTL activity to the patient's autologous tumor.

(4) BCG activates innate immune receptors, primarily TLR, within the endothelial lining of the bladder following intravesical administration. Activation of these innate receptors contributes to the local production of inflammatory cytokines, including IL-1 $\beta$  and TNF $\alpha$ , which provide an inflammatory signal leading to upregulation of the local microvascular endothelium within the bladder wall, including expression of selectin ligands and integrins, such as ICAM-1 and VCAM-1.

Vesigenurtacel-L is administered intradermally and leads to the activation of antigen-specific CD8+ T cells that circulate through the systemic vasculature. Extravasation of T cells into tissues requires activation of endothelial cells, and trafficking through inflamed vessels is mediated by selectins, integrins, and chemokines. Thus, the systemic activation of T cells by vesigenurtacel-L is proposed to synergize with BCG through the combined increase in bladder-tumor antigen-specific T cells that may traffic more efficiently into the bladder due to endothelial activation by locally administered BCG.

Similarly, inflammation generated in response to the TURBT surgical procedure may drive CD8+ T cells into the bladder tissue, even in the absence of BCG, mediating CD8+ T cell trafficking to the bladder in a BCG-independent fashion. Initiating vaccination during the perioperative period immediately after TURBT potentially capitalizes on this period of post-operative immunoactivity.

(5) In current clinical practice, no treatment is typically administered during the 6 week period following completion of BCG induction therapy and prior to the next cystoscopy. Continued treatment with a vaccine, such as vesigenurtacel-L, during this time may provide an additional important window for continued immune stimulation, which could result in improved treatment response.

(6) Although it is postulated that concurrent administration of intravesical BCG and intradermal vesigenurtacel-L might result in optimally synergistic immunoactivation, it is also possible that intradermal vesigenurtacel-L monotherapy will result in a significant degree of immune modulation, independently of concomitant BCG. The current study will, therefore, examine vesigenurtacel monotherapy in patients who will not receive BCG.

### **1.3 Description of Investigational Agent Vesigenurtacel-L**

Vesigenurtacel-L is a whole cell vaccine that has been irradiated to render cell replication incompetent while maintaining biological activity, i.e., expression of certain tumor-associated antigens as described above.

Vesigenurtacel-L is derived from a human prostate cancer cell line, PC3. This cell line was evaluated amongst others and was selected based on the overlap of its native antigenic profile with that of tumor

samples from patients with NMIBC. The chosen PC3 tumor cells were modified to express HLA-A1 protein and secrete gp96-Ig fusion protein by stable transfection. Clones with a high level of expression were obtained by G418 (Geneticin) selection and flow cytometry cell sorting.

Preparation of the drug product includes expansion of batches of cells using current good manufacturing practices (cGMP) manufacturing methods. The cells are tested for presence of expression of HLA-A1 by fluorescent-activated cell sorter (FACS) and gp96-Ig expression by enzyme-linked immunosorbent assay (ELISA). Cells are harvested, washed, resuspended in buffered saline, irradiated, washed and vialled. The vialled cells are frozen and then stored at  $\leq -120^{\circ}\text{C}$  in the vapor phase of a liquid nitrogen freezer.

## 1.4 Prior Human Experience

This is the first trial to dose patients with vesigenurtacel-L. A first-in-human Phase 1 study of HS-110, a lung cancer vaccine using the same technology platform, was conducted in 18 patients with advanced non-small cell lung cancer (NSCLC). Patients received one of three dosing regimens. Safety was evaluated as a primary endpoint and tumor response and survival were secondary endpoints. Immune response in peripheral blood was characterized in 15 patients who received at least one course (6 weeks) of vaccination by measuring production of IFN- $\gamma$  by patient CD8+ T cells as compared to baseline.

The majority of adverse events were mild injection site reactions, consisting mainly of rash, induration, pruritus, and pain. Six serious adverse events were reported for five patients: respiratory disorder for a patient who was enrolled but not treated with HS-110, disease progression (two patients), chest pain, and dyspnea and rectal hemorrhage. None of these events was considered by the investigator to be treatment-related.

None of the 18 patients had an objective tumor response by the Response Evaluation Criteria in Solid Tumors (RECIST). Fourteen patients had died, and four surviving patients were followed for a median of 10.6 months (range 2.6 to 16.6). The Kaplan-Meier estimate of median survival was 8.0 months (95% confidence interval [CI]: 6.7 to 18.2), and the 6, 12, and 24-month overall survival (OS) rates were 77.8% (95% CI: 51.1 to 91.0%), 41.9% (95% CI: 19.1 to 63.3%), and 11.2% (95% CI: 0.8 to 37.3%), respectively. All patients have now died.

## 2.0 OBJECTIVES

### 2.1 Primary Objective

#### Phase 1

To characterize the safety and tolerability of low dose monotherapy vaccination with vesigenurtacel-L in patients with non-muscle invasive bladder cancer

#### Phase 2

- Arms 1, 2, and 3: To evaluate 1-year disease-free survival in patients with non-muscle invasive bladder cancer treated with BCG in combination with blinded study product (one of two doses of vesigenurtacel-L or placebo)
- Arm 4: To evaluate 1-year disease-free survival in patients with non-muscle invasive bladder cancer treated with high dose vesigenurtacel-L monotherapy

## 2.2 Secondary Objectives

- To evaluate the safety of the combination of vesigenurtacel-L and BCG (Phase 2 only)
- To evaluate the safety of high dose vesigenurtacel-L monotherapy (Phase 2 only)
- To evaluate the proportion of patients with recurrence at 3, 6, 12, 18, and 24 months
- To evaluate the proportion of patients with progressive disease at 3, 6, 12, 18, and 24 months
- To evaluate disease-free survival at 3, 6, 18, and 24 months
- To evaluate overall disease-free survival
- To evaluate overall survival (OS)
- To evaluate the proportion of patients undergoing post-treatment TURBT or fulguration by 12 and 24 months
- To evaluate the proportion of patients undergoing cystectomy by 12 and 24 months
- To evaluate the proportion of patients with immunologic response of PBMCs via intracellular cytokine staining (ICS) by flow cytometry and/or ELISPOT on CD8+ cells following vesigenurtacel-L vaccination

## 2.3 Exploratory Objectives

- Immunologic response of PBMCs (analysis of surface markers, CD3, CD4, CD8, CD19, CD25, CD45, CD56, FoxP3, and degranulation) and stimulation analysis via ICS of IFN $\gamma$  and granzyme B (gzB)
- Total PBMC counts by flow cytometry, including lymphocyte subsets (B cells, helper T-cells, cytotoxic T-cells, NK cells and T-reg)
- Evaluation of tumor tissue obtained prior to treatment for antigen expression, expression of major histocompatibility complex (MHC) class I, and expression of immunosuppressive molecules
- Evaluation of tumor tissue obtained from repeat biopsy, if clinically indicated, for presence of tumor infiltrating T-lymphocytes (TILs)
- T cell receptor sequencing of PBMCs and tumor tissue to determine correlation between clonally expanded T cell populations and other endpoints
- Immune cell infiltration and inflammatory cytokine levels in urine (Phase 2 only)

[figure not shown]
## 3.0 TRIAL DESIGN

### 3.1 Study Design Overview

This is a multi-center, randomized, placebo-controlled study consisting of two phases as shown in Figure 1 below.

**Figure 1. Study Design**

Patients with non-muscle invasive bladder cancer who have either undergone TURBT or fulguration for the removal of papillary disease or who have carcinoma in situ (CIS) only, are candidates for BCG treatment, and are judged to be at an increased risk for recurrence are eligible if they are BCG naive or have completed previous BCG treatment >12 months prior to the baseline staging procedure. Phase 2 also allows patients who will not otherwise receive BCG.

The Phase 1 portion is an open-label, safety study consisting of one cohort with 10 patients. Patients will have previously received 3-6 instillations of weekly intravesical BCG induction therapy (as standard of care) followed by low dose intradermal ( $1 \times 10^6$  cells) vesigenurtacel-L monotherapy.

In Phase 2, patients will be assigned to treatment groups based on whether they will receive induction BCG in the typical post-TURBT window. If the investigator plans to administer BCG, patients will be randomized to one of three blinded (physician-patient), placebo-controlled groups and receive either intradermal placebo or low dose or high dose ( $1 \times 10^7$  cells) vesigenurtacel-L in combination with induction and maintenance intravesical BCG. If patients will not receive BCG, they will be enrolled into an open-label, non-randomized group and receive high dose intradermal vesigenurtacel-L monotherapy.

**Phase 1:** Patients enrolled in the first cohort within 8-10 weeks of TURBT or fulguration for patients with papillary disease and staging procedure for patients with CIS only and after induction BCG will be treated with vesigenurtacel-L weekly for 6 weeks. After a one-week vaccine holiday for disease assessment, patients will receive vesigenurtacel-L for an additional 6 weeks followed by three once monthly treatments for a total of 15 vaccinations. Patients will be observed weekly to assess the safety of vesigenurtacel-L. Dosing of the first three patients will be staggered by two-week intervals to allow for safety evaluation before treating additional patients. If vesigenurtacel-L appears safe and well-tolerated in the 3 lead-in patients, dosing will be continued to 10 patients.

Phase 2: Dosing in Phase 2 will begin when all 10 patients have been dosed in the Phase 1 cohort, at least 6 patients in that cohort have completed the Week 7 safety assessments, and the Data Monitoring Committee (DMC) has met to review this data and agreed it is safe to advance to Phase 2. A total of 100 patients will be assigned to four groups: 75 who will receive BCG will be randomized to arms combining either low dose vesigenurtacel-L, high dose vesigenurtacel-L, or placebo, respectively, with induction and maintenance BCG; 25 who will not receive BCG will be enrolled in the high dose vesigenurtacel-L monotherapy arm.

In the randomized arms, treatment will commence within 6 weeks of the most-recent TURBT or fulguration for patients with papillary disease and staging procedure for patients with CIS only. Patients will be treated during an induction phase with weekly intravesical BCG and intradermal blinded study product (vesigenurtacel-L or placebo) for 6 weeks followed by 6 weekly injections of blinded study product alone. During a subsequent maintenance phase, patients will receive an additional three courses of three once-weekly blinded study product injections in combination with intravesical BCG approximately 3, 6, and 12 months after initiating induction BCG. Patients may receive additional courses of maintenance BCG in long-term follow-up at the investigator's discretion but should not receive any other cancer therapy prior to disease recurrence/progression.

In the monotherapy arm, treatment will commence within 6 weeks of the most-recent TURBT or fulguration for patients with papillary disease and staging procedure for patients with CIS only. Patients will be treated during an induction phase with weekly intradermal vesigenurtacel-L for 12 weeks. During a subsequent maintenance phase, patients will receive an additional three courses of three once-weekly vesigenurtacel-L injections approximately 3, 6, and 12 months after initiating induction vesigenurtacel-L.

All patients in both the Phase 1 and Phase 2 portions of the study will have a cystoscopy and cytology and, if clinically indicated, a biopsy performed approximately every 3 months for 2 years then every 6 months for up to a year, study termination, disease progression, or recurrence requiring treatment discontinuation, whichever occurs first. Patients with evidence of disease at an assessment may continue on treatment if judged by the investigator to be in the patient's best interest (e.g. would normally receive another course of BCG therapy as standard of care (SOC)). Upon discontinuation of study treatment, additional treatment will be at the discretion of the treating physician per SOC. While treatment may continue in the presence of evidence of disease, statistical analysis of disease-free status will still follow strict definitions as defined in section 10.1 Evaluation of Disease.

### **3.2 Justification of Study Product Administration Strategy**

A clinical trial of a similar vaccine for lung cancer derived from the same proprietary technology as the vaccine for this study examined three dosing schedules: twice weekly, weekly, and once every two weeks. The twice weekly and weekly dosing schedules were determined to produce the most desirable immune response in peripheral blood (at least a doubling of CD8 from baseline). The weekly dosing schedule was selected for this trial as it was determined to provide reasonable patient acceptability for frequency of treatment visits and concordance with the standard BCG dosing schedule.

Two doses were selected ( $1 \times 10^6$  cells and  $1 \times 10^7$  cells) for this study. The  $1 \times 10^7$  cell dose was selected based on the number of cells needed to produce an equivalent amount of gp96-Ig to that used in the lung cancer vaccine. Additionally, murine data suggest that lower doses may produce a sufficient immune

response and may even result in superior clinical effects, and therefore, the lower dose of  $1 \times 10^6$  cells was included as one of the two doses for evaluation in this trial.

Study product will be administered weekly as the number of intradermal injections required to reach the number of cells per dose with no more than 0.1mL per injection (see Section 8.3). The selection of the route of administration is based on the hypothesis that split doses stimulate stronger immune responses by allowing vaccine antigens to reach more regional lymph nodes (where immune responses are generated). Vesigenurtacel-L will be administered intradermally to enhance stimulation of cellular immune responses as compared to subcutaneous or intramuscular immunization.

### **3.3 Number of Subjects**

Approximately 110 patients will be enrolled from up to 20 clinical trial centers. In Phase 1, 10 patients will be enrolled in a single cohort given treatment with monotherapy low dose vesigenurtacel-L. In Phase 2, 25 patients will be enrolled in each of four arms: low dose vesigenurtacel-L in combination with BCG, high dose vesigenurtacel-L in combination with BCG, placebo in combination with BCG, and high dose vesigenurtacel-L monotherapy (100 patients total).

### **3.4 Study Endpoints**

#### **3.4.1 Primary Efficacy Endpoint**

Phase 1: Safety and tolerability

Phase 2: 1-year Disease-Free Survival (1-yr DFS)

#### **3.4.2 Secondary Endpoints**

- Safety of the combination of vesigenurtacel-L and BCG (Phase 2 only)
- Safety of high dose vesigenurtacel-L monotherapy (Phase 2 only)
- Proportion of patients with recurrence at 3, 6, 12, 18, and 24 months
- Proportion of patients with progressive disease at 3, 6, 12, 18 and 24 months
- Disease-free survival (DFS) at 3, 6, 18, and 24 months
- Overall DFS
- Overall Survival (OS)
- Proportion of patients undergoing post-treatment TURBT or fulguration by 12 and 24 months
- Proportion of patients undergoing cystectomy by 12 and 24 months
- Proportion of patients with immunologic response of PBMCs via intracellular cytokine staining (ICS) by flow cytometry and/or ELISPOT on CD8+ cells after receiving vesigenurtacel-L treatment as compared to baseline

#### **3.4.3 Exploratory Endpoints**

- Immunologic response of PBMCs (analysis of surface markers, CD3, CD4, CD8, CD19, CD25, CD45, CD56, FoxP3, and degranulation) and stimulation analysis via ICS of IFN $\gamma$  and gzB
- Total PBMC counts by flow cytometry, including lymphocyte subsets (B cells, helper T-cells, cytotoxic T-cells, NK cells and T-reg)

- Evaluation of tumor tissue obtained prior to treatment for antigen expression, expression of major histocompatibility complex (MHC) class I, and expression of immunosuppressive molecules by mRNA expression and/or immunohistochemical analysis
- Evaluation of tumor tissue obtained from repeat biopsy, if clinically indicated, for presence of infiltrating T-lymphocytes (TILs)
- T cell receptor sequencing of PBMCs and tumor tissue to determine correlation between clonally expanded T cell populations and other endpoints
- Immune cell infiltration and inflammatory cytokine levels in urine (Phase 2 only)

### 3.5 Study Termination Criteria

The sponsor may terminate the study at any time on the basis of safety considerations or other factors that may be deemed to affect the scientific validity or ethical viability of the protocol.

## 4.0 PARTICIPANT SELECTION

### 4.1 Inclusion Criteria

Patients must meet all of the following inclusion criteria to be enrolled into the study:

1. Willing and able to sign informed consent and comply with the protocol, including clinic visits to receive weekly vesigenurtacel-L injections for 12 doses followed by either monthly vesigenurtacel-L injections for three months in Phase 1 or three courses of three once-weekly injections in Phase 2.
2. Histologically or cytologically confirmed non-muscle invasive bladder cancer [Ta, T1 or Tis (CIS)]. Papillary disease must have been removed by transurethral resection or fulguration.
3. Either
  - i. High-risk disease, defined as T1 and/or high-grade and/or CIS, *or*
  - ii. Intermediate-risk disease defined as Ta low-grade with at least three of the following four risk factors: multiple tumors, tumor size > 3cm, early recurrence (<1 year from previous staging procedure), or recurrence with a frequency of more than once in any 12 month period.
4. Patients must be BCG naive or have completed previous BCG treatment >12 months prior to the baseline staging procedure.
5. For Phase 2 only: Arms 1, 2, and 3: Suitable, in the opinion of the investigator, to receive a 6-week course of induction intravesical BCG in the adjuvant setting within 6 weeks following the baseline staging procedure for the current occurrence of non-muscle invasive bladder cancer. Arm 4: Suitable for monotherapy vaccine administration post-TURBT. For Phase 1 only: Has previously received 3-6 weekly doses of BCG.
6. Age  $\geq$ 18 years
7. Lab parameters:

- Albumin  $\geq 2.5$  mg/dL
  - Total bilirubin  $< 1.5$  mg/dL
  - Alanine transaminase (ALT) and aspartate transaminase (AST)  $\leq 2.5 \times$  upper limit of normal (ULN)
  - Serum creatinine  $\leq 2.2$  mg/dL or calculated creatinine clearance  $> 35$  mL/minute per the Cockcroft-Gault formula
  - White blood cell (WBC) count  $\geq 4,000/\text{mm}^3$  with an absolute neutrophil count  $\geq 1,500/\text{mm}^3$
  - Hemoglobin  $\geq 9$  g/dL
  - Platelet count  $\geq 75,000/\text{mm}^3$
8. Women of childbearing potential or men of fathering potential must use adequate birth control measures (e.g., abstinence, oral contraceptives, intrauterine device, barrier method with spermicide, or surgical sterilization) during the study and for 6 months after receiving the last administration of study medication. Female patients of childbearing potential must test negative for pregnancy prior to enrolling in the trial.

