Eligibility criteria:	Inclusion Criteria: 

1. Willing and able to sign informed consent and comply with the protocol, including clinic visits to receive weekly vesigenurtacel-L injections for 12 doses followed by either monthly vesigenurtacel-L injections for three months in Phase 1 or three courses of three once-weekly injections in Phase 2.

2. Histologically or cytologically confirmed non-muscle invasive bladder cancer [Ta, T1 or Tis (CIS)]. Papillary disease must have been removed by transurethral resection or fulguration.

3. Either

i. High-risk disease, defined as T1 and/or high-grade and/or CIS, or

ii. Intermediate-risk disease defined as Ta low-grade with at least three of the following four risk factors: multiple tumors, tumor size > 3cm, early recurrence (<1 year from previous staging procedure), or recurrence with a frequency of more than once in any 12 month period

4. Patients must be BCG naïve or have completed previous BCG treatment >12 months prior to the baseline staging procedure.

5. For Phase 2 only: Arms 1, 2, and 3: Suitable, in the opinion of the investigator, to receive a 6-week course of induction intravesical BCG in the adjuvant setting within 6 weeks following the baseline staging procedure for the current occurrence of non-muscle invasive bladder cancer. Arm 4: Suitable for monotherapy vaccine administration post-TURBT. For Phase 1 only: Has previously received 3-6 weekly doses of BCG.

6. Age ≥18 years

7. Lab parameters:

○ Albumin ≥2.5 mg/dL

○ Total bilirubin <1.5 mg/dL

○ Alanine transaminase (ALT) and aspartate transaminase (AST) ≤2.5 × upper limit of normal (ULN)

○ Serum creatinine ≤2.2mg/dL or calculated creatinine clearance >35 mL/minute per the Cockcroft-Gault formula

○ White blood cell (WBC) count ≥4,000/mm^3 with an absolute neutrophil count ≥1,500/mm^3

○ Hemoglobin ≥9 g/dL

○ Platelet count ≥75,000/mm^3

8. Women of childbearing potential or men of fathering potential must use adequate birth control measures (e.g., abstinence, oral contraceptives, intrauterine device, barrier method with spermicide, or surgical sterilization) during the study and for 6 months after receiving the last administration of study medication. Female patients of childbearing potential must test negative for pregnancy prior to enrolling in the trial.

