### 11.2 Clinical Laboratory Tests

Patients will have blood samples collected for routine clinical laboratory testing. The clinical laboratory parameters will be analyzed at the site's local laboratory. Laboratory assessments to be completed will include hematology, chemistry, and urine or serum pregnancy test (females of childbearing potential).

Laboratory assessments will be defined as follows:

- **Chemistry:** To include sodium, calcium, total protein, albumin, creatinine, blood urea nitrogen, total bilirubin, alkaline phosphatase, AST, ALT, potassium, chloride, bicarbonate, lactate dehydrogenase, and glucose.
- **Hematology:** To include white blood cell (WBC) with differential, platelet count, hemoglobin, and red blood cell (RBC) count.
- **Urine or serum pregnancy test** – See section 11.7 below for further details.

Additional laboratory assessments may be conducted throughout the study as medically necessary.

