Revisions to the statistical sections (analysis populations, sample size justification) etc.	Synopsis, Sections 12.X	Version 3.0, Amendment 2
Revise the dose escalation process such that the DEC will convene after at least one patient has received 6 vaccine doses and at least three patients have received two doses.	Synopsis, Sections 3.1, 5.1.1	Version 3.0, Amendment 2
Extend window of beginning of treatment from 8-10 weeks post-TURBT to 8-12 week post-TURBT.	Synopsis, SOE, Section 3.1	Version 3.0, Amendment 2
Change "enrollment" to "dosing" in description of dose escalation for clarity	Synopsis, Section 3.1, 5.2.2	Version 3.0, Amendment 2
Add detail in Appendix 2 to provide additional clarity about staging requirement	Appendix 2	Version 3.0, Amendment 2
Remove section 3.3 as duplicative to section 3.1	Section 3.3	Version 3.0, Amendment 2
Change regimen in Phase 1 and Phase 2	Synopsis, Section 3.1, Section 6.0, Section 8.5, Section 12.1	Version 4.0, Amendment 3
Define a BCG maintenance schedule	Synopsis, Section 3.1, Section 8.5.1, Section 8.5.2	Version 4.0, Amendment 3
Allow a single post-TURBT instillation of intravesical chemotherapy	Section 9.1	Version 4.0, Amendment 3
Analyze recurrence separately from progression	Section 10.1	Version 4.0, Amendment 3
Define persistent disease for patients with CIS	Section 10.1	Version 4.0, Amendment 3
Define the dose of BCG	Section 8.4, Section 8.5.2	Version 4.0, Amendment 3
Modify window between TURBT and start of treatment	Synopsis, Section 3.1, Section 6.2.1	Version 4.0, Amendment 3

Protocol Change	Section Affected	Version where implemented
Require 5 of 6 cycles of induction BCG	Section 8.4	Version 4.0, Amendment 3
Changed criteria for CrCl, albumin, and platelet laboratory parameters	Synopsis, Section 4.1	Version 4.0, Amendment 3
Adopt the standard definition of high-risk disease (T1 and/or high grade and/or CIS)	Synopsis, Section 4.1, Appendix 1	Version 4.0, Amendment 3
Exclude patients with prior prostatic pelvic radiation within the past 12 months	Synopsis, Section 4.2	Version 4.0, Amendment 3
Exclude patients with neo-adjuvant therapy prior to the most recent TURBT	Synopsis, Section 4.2	Version 4.0, Amendment 3
Exclude patients with allergy to peanuts	Synopsis, Section 4.2	Version 4.0, Amendment 3
Reduce time window for cardiac exclusion from previous 6 months to 3 months	Synopsis, Section 4.2, Appendix 2	Version 4.0, Amendment 3

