6.3 Demographic and Baseline Variables

For both the phase 1 and 2 parts of the study, the following patient baseline demographics and disease status variables will be summarized by treatment group for the ITT Population:

Demography: Age, sex, race and ethnicity

Stratification factors: Risk of recurrence (High risk vs intermediate risk), carcinoma in situ (yes vs no)

Bladder cancer history: histopathologic type, TNM stage, carcinoma in situ, severity, newly diagnosed disease vs recurrent disease, time from last BCG treatment to screening (for patients with recurrent disease)

Phase 1 Risk assessment: Number of tumors, tumor diameter, prior recurrence rate, category (Ta / T1), concurrent CIS, Grade (WHO 1973), total recurrence score, total progression score

Baseline vital signs: Weight, height, systolic blood pressure, diastolic blood pressure, heart rate, body temperature and respiratory rate

Selected baseline laboratory, including lab values dictating inclusion/exclusion:

- Hematology: White blood cell (WBC) count, neutrophils, platelets, hemoglobin, lymphocytes, red blood cell (RBC) count
- Chemistry: ALT, AST, Alkaline phosphatase, Albumin, total bilirubin, serum creatinine, creatinine clearance

No statistical tests to check homogeneity between treatment groups at baseline will be performed.

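### The albumin entry limit is written in mg/dL in all three places, so read literally this mandatory criterion excludes nobody

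*Protocol*

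**What the plan says.** Protocol 4.1 introduces its list with "Patients must meet all of the following inclusion criteria to be enrolled into the study". Criterion 7 then gives the laboratory limits, among them "Albumin $\geq 2.5$ mg/dL". The synopsis has the same limit, "Albumin ≥2.5 mg/dL", and SAP 3.3 repeats it with the same number and unit.

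The same list uses mg/dL for bilirubin and creatinine. For another blood protein it uses grams: "Hemoglobin ≥9 g/dL".

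Three other places bear on how the limit is used:
- Protocol 11.2: "The clinical laboratory parameters will be analyzed at the site's local laboratory". Protocol 3.3 allows up to 20 centers.
- SAP 6.3 summarises albumin under the heading "Selected baseline laboratory, including lab values dictating inclusion/exclusion".
- Protocol 13.3 and SAP 6.2 make enrolment of a patient who did not meet the entry criteria a captured deviation, and SAP 6.2 has it reviewed for its effect on the per-protocol population.

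**The concern.** A lower limit on a laboratory value is useful only if some candidates can fall below it. At 2.5 mg/dL none plausibly can, because serum albumin is of the order of grams per decilitre. The slip is in the decision threshold itself, not in background text, and it was carried unchanged into the SAP.

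Three things are at stake, all of them about eligibility and the record of it:
- The written criterion does no work. A patient with very low albumin satisfies it.
- The deviation category for ineligible patients cannot be reached through albumin, because compliance is judged against the written text.
- Albumin is measured locally and the text does not say what was meant. A site that applies the words and a site that silently changes the unit would be using different entry rules. A patient refused at, say, 2.0 g/dL would have been refused while meeting the criterion as written.

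**Working it through.** There is no derived figure to reproduce. The limit is a stated threshold, so the check is a unit conversion and a comparison of the places where it appears.

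**1. Is it a reading error in one place?** The limit appears in the protocol synopsis, Protocol 4.1 and SAP 3.3. These are three current statements in two documents, laid out differently, and all three give 2.5 with mg/dL. No current text gives albumin in another unit. A fault in reading one page does not explain this.

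**2. Conversion.** 1 g/dL = 1,000 mg/dL, so 2.5 mg/dL ÷ 1,000 = 0.0025 g/dL.

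**3. Comparison with plausible values.** The documents give no albumin range. *Assumption:* 1.0 to 5.5 g/dL, from severe hypoalbuminaemia to high normal. The ratio is (value in g/dL × 1,000) ÷ 2.5.

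| Assumed albumin (g/dL) | In mg/dL | Multiple of the written limit | Meets the limit as written | Meets the same number if read in g/dL |
|---|---|---|---|---|
| 1.0 | 1,000 | 400 | yes | no |
| 2.0 | 2,000 | 800 | yes | no |
| 2.5 | 2,500 | 1,000 | yes | yes |
| 3.5 | 3,500 | 1,400 | yes | yes |
| 4.0 | 4,000 | 1,600 | yes | yes |
| 5.5 | 5,500 | 2,200 | yes | yes |

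The limit is therefore 1/400 to 1/2,200 of a patient's value over the assumed range. The result does not hinge on that range: at 0.5 g/dL the value is still 500 ÷ 2.5 = 200 times the limit. The last column only shows what the unit does to the criterion. It is not a proposal for the limit.

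**4. Was albumin a live criterion?** The revision history in Protocol Appendix 4 records "Changed criteria for CrCl, albumin, and platelet laboratory parameters". This is history and not evidence of an error, but it shows that the sponsor set the albumin limit deliberately. SAP 6.3 likewise treats albumin as one of the values that decide entry.

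**5. What does it reach in the analysis?** Albumin is not a stratification factor (SAP 3.4), not part of the primary endpoint (Protocol 12.5.1, SAP 7.1) and not an input to the sample size (Protocol 12.6.2, SAP 4). The primary analysis is by intention to treat (SAP 5.2.2 and 7.1). The only analysis link is the eligibility deviation and, through it, the per-protocol population.

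**The case against.** The strongest reply is that this is an evident slip that any clinician would read as g/dL, so nothing went wrong in practice. That may be so, and nothing in the documents contradicts it; equally, nothing confirms it. A reader might infer that a safety screen failed and that unsuitable patients were enrolled. The documents do not support that. They state no purpose for the albumin limit, contain no record of how sites applied it, and give no albumin distribution from which to count the candidates who would fall below a corrected limit. If almost none would, the two readings admit nearly the same patients.

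The second reply is that the consequences are small, and this largely stands. Per-protocol re-analyses are exploratory (SAP 7.3). Exclusion from that population needs a major deviation judged to bear on efficacy (SAP 5.2.2). Low values would also stay visible, because albumin is summarised at baseline (SAP 6.3) and, where applicable, graded and shown in shift tables (SAP 8.4).

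The third reply concerns the remedy, and it stands in full. Protocol 13.3 defines a deviation as departure from the approved protocol. A patient enrolled under the written limit complied with it, so a corrected limit cannot make that patient a deviation afterwards. Nor do the documents describe an electronic check on albumin; SAP 5.4 mentions only general programs for out-of-range data. It should not be assumed that a faulty check exists.

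None of this rescues the written text. Eligibility is judged against it, and in all three places it gives a limit that cannot exclude anyone.

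**Conclusion.** The point holds as an error in a decision threshold. The written limit is 0.0025 g/dL, which is 1/400 to 1/2,200 of a patient's albumin if albumin lies between 1.0 and 5.5 g/dL. That range is an assumption from outside the documents, but the conclusion survives any plausible choice. Read literally, the criterion is met by everyone, and the matching eligibility deviation cannot arise from albumin.

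The effect stops there. The primary analysis, sample size and power are untouched. How many patients, if any, were admitted who would otherwise have been excluded cannot be estimated from the documents, nor can it be said how sites read the unit.

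**What to change.** The sponsor should confirm the intended albumin limit and its unit, and correct criterion 7 in the protocol synopsis, Protocol 4.1 and SAP 3.3 together so that the three agree. If an edit check uses the limit, it should be brought into line at the same time. No value is proposed here.

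For patients already enrolled, list baseline albumin against the confirmed limit as description only. Patients who met the approved text should not be reclassified as eligibility deviations, and the per-protocol population should not change on this account.

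The cost is a minor protocol amendment with the matching SAP correction, and one data listing from values already collected.
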